8.1.3 Packaging, Labelling and Supply (re-supply)

Non-applicable.

8.1.4 Storage Conditions

Non-applicable.

8.2 Administration of experimental and control interventions

The intervention and control messages will be delivered by a standardised audio recording in the first phase of the study and then directly by the caregivers themselves in the second phase.

In the first phase of the study, caregivers will prepare patients for the PIC insertion according to the usual procedure (placement of tourniquet, vein tracking and site disinfection). As soon as these preparations are completed, the co-investigators will play the audio message recorded intervention or control to the patients. The end of the audio message will instruct patients to lift a finger from their other hand and, at that point, the caregivers will sting them and complete their procedure.

In the second phase, the message will be delivered by the caregivers themselves just before they sting the patients.

8.3 Dose / Device modifications

Non-applicable.

8.4 Compliance with study intervention

In order to ensure that the recorded messages are not perceived as artificial by patients, the audio recordings were tested and adapted until they were perceived as adequate in a « Messages » pilot phase.

Emergency care staff will be informed of the progress of the study and the content of the messages during one of their monthly team meeting, which will then be the subject of a report sent to the entire team. They will be asked to act naturally with patients during the procedure, without referring to the current study for the duration of the procedure, nor commenting early on the PIC placement. When the second phase of the study begins, emergency care staff will be more accurately informed and trained by co-investigators on how to deliver the messages.

Differences in the script, patient or caregiver interventions will be reported in the CRF under the « Difficulty(-ies) encountered » category for inclusion in the data analysis but will not be grounds for exclusion from the study. The same will be true in the second phase for variations in the messages delivered by caregivers. They will be reported in the CRF under the « Verbal script » category but will not constitute grounds for exclusion from the study.

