6.2.2 Blinding procedures

During the first phase, the allocation of the arm « control message » or of the arm « intervention message » will be determined by a code written on a card inside a sealed and opaque envelope, prepared by the principal investigator. This code will indicate the number, between 1 and 130, of the audio track to be played to the patient and will be recorded in the CRF. In the second phase, the note « control message » or « intervention message » written on the card will indicate to the caregivers the message to be delivered and will be reported in the CRF. Envelopes will be numbered consecutively, and the co-investigators will open them consecutively, noting each time the opening date. The principal investigator will regularly verify that the order of opening is respected by checking the number of envelopes opened and the opening dates against the number of patients included in the study.

The first phase of the study will be carried out in double blind (patient, caregiver, co-investigator) thanks to the coding of audio recordings. In the second phase, only patients will be blinded to the tested component.

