6.2.3 Other methods of minimising bias

Based in particular on the limitations identified from the studies included in the 2015 systematic review (Mistiaen et al., 2016), the following measures were taken to minimize as much as possible the bias that could result from this study:

- Integrity of the intervention: most of the studies included in the systematic review had not verified the accuracy of their intervention. In both phases of our study, caregiver behaviour will be reported in the CRF according to Kaptchuck criteria. In the first phase of the study, caregivers will be instructed to act naturally with patients during the procedure, without referring to the ongoing study throughout the entire duration of the procedure or commenting early on the PIC placement. Any interactions will be reported in the CRF under the « Difficulty(-ies) encountered » category. In the second phase, the script as it has been verbalized by the caregivers will also be globally reported. The content of the message delivered by caregivers will be reported in writing to the CRF as key words/concepts, checked off once they have been stated. For key words/concepts that would not be included in the original script, but which would still be mentioned by caregivers, they will be reported specifically under the « Other(s) » category. We have also scheduled for each phase an information session for the emergency care staff on the progress of the study and the content of the messages at one of their monthly team meeting, which will then be the subject of a report sent to the entire team;
- Statistical considerations: most of the studies included in the systematic review had not calculated an *a priori* statistical power, and since many studies included a small number of patients (from 19 to 771 with an average of 110 patients per study), divided into several intervention arms, the probability was high that a real effect could not be detected. We calculated an *a priori* statistical power in our study and set a minimum number of participants at 240;
- Retention of baseline demographic data (sex, age) of patients who have revoked consent or who were excluded from the study to ensure that they are similar to patients included on these

two criteria;

- Intervention control not described: we plan to transcribe the texts of the messages intervention and control in the presentation of the results of the study;

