8.1.1 Experimental Intervention

First phase - Text of the recorded intervention message:

In the « intervention message » arm, the recorded message will be:

« It is possible that this arm may begin to feel a certain numbness, a kind of heaviness, or warmth, as if it was asleep during the procedure. Now that you've heard this message, you can signal the caregiver as soon as you're ready by lifting a finger from your other hand. »

The key elements are: dissociation of the arm, being ready, sense of control, anesthetic suggestion limited to the duration of the procedure.

Second phase - Text of the intervention message delivered by caregivers:

In order for the intervention to be credible, it is important that caregivers take ownership of the message to be delivered. Caregivers will then receive the original text, along with the key elements it contains and the contradictory elements to be omitted. They will be encouraged to formulate a variant that fits them but contains these key elements. A reminder of key elements will be provided at each clinical interaction. Some deviations from the script will be tolerated as long as the essential content of the message to be delivered is preserved and no contradictory elements are inserted. The content of the messages delivered by caregivers will be reported in writing in the CRF by the co-investigator in the form of key words/concepts, checked off once they have been stated. For key words/concepts that would not be included in the original script, but which would still be mentioned by caregivers, they will be reported specifically under the « Other(s) » category.

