8.1.2 Control Intervention

First phase - Text of the recorded control message:

In the « control message » arm, the recorded message will be:

« You may feel the tourniquet on your arm, it's tight, maybe it's tingling. Stinging can hurt when the needle goes in, but don't move during the procedure. When this message stops, lift a finger from your other hand and the caregiver will sting you. »

The key elements are: contact with the tourniquet and its sensory aspect, then sensory aspects of the needle, lack of control.

Second phase - Text of the control message delivered by caregivers:

Similar to the text of the intervention message delivered by the caregivers in section 8.1.1 « Experimental intervention ».

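### Phase 1 caregivers are briefed on message content they do not need, which leaves their blind open to inference from the timing of the patient's signal

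*Combined protocol and SAP*

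**What the plan says.** Section 6.2.2 describes phase 1 as double blind for patient, caregiver and co-investigator, and attributes this to the coding of the audio recordings. Section 3.1 gives the reason for wanting that blind: a caregiver who knows the message may, more or less consciously, behave in a way that matches it.

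On briefing, Section 8.4 states: "Emergency care staff will be informed of the progress of the study and the content of the messages". This happens at a monthly team meeting, followed by a report to the whole team. Section 6.2.3 shows that phase 1 is included, because the plan has "scheduled for each phase an information session for the emergency care staff on the progress of the study and the content of the messages". More detail follows later: "When the second phase of the study begins, emergency care staff will be more accurately informed and trained".

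The closing instructions of the two recordings differ. In the intervention arm (Section 8.1.1) the patient hears "you can signal the caregiver as soon as you're ready by lifting a finger from your other hand". In the control arm (Section 8.1.2) the patient hears "When this message stops, lift a finger from your other hand and the caregiver will sting you".

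Sections 7.1 and 7.4 exclude a phase 1 patient if the caregiver or co-investigator learns the assigned message before the intervention. Section 5.2 makes the caregivers' ratings of the patient's pain intensity, unpleasantness and anxiety secondary outcomes.

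**The concern.** Coding the tracks hides the assignment. It does not stop a caregiver from working it out at the bedside. The caregiver has prepared the arm and is waiting for the finger to go up. A caregiver who knows that one message lets the patient choose the moment, while the other ties the signal to its end, has a way to interpret a prompt or a delayed signal. A caregiver who does not know the content would see only a finger being lifted.

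Two things are at stake. First, the caregiver rates pain and anxiety after having seen the signal, so an inferred arm could colour those ratings, and could also colour behaviour during the puncture. That is the bias that the audio phase was designed to remove. Second, staff who have learned the positive wording may carry it into their ordinary talk with patients in both arms, which would reduce the contrast between the messages.

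**Working it through.** The plan gives no figure on this point, and its sample size of 55 per arm before the allowance for losses does not depend on it. The check is a reading of the sections against each other.

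1. **Does the content briefing cover phase 1?** Yes. The sentence in Section 8.4 does not name a phase, but Section 6.2.3 schedules a session for each phase and lists message content among its topics.

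2. **How much content is given in phase 1?** This is not specified. Section 8.4 says that fuller information and training come with phase 2. The statement "Caregivers will then receive the original text, along with the key elements it contains" appears in Section 8.1.1 only under the second phase. Phase 1 staff are therefore told the content at some level of detail, but the plan does not say that they receive the scripts.

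3. **Is there a cue that such knowledge would make readable?** Possibly. Section 8.2 describes the same gesture in both arms, a finger of the other hand. What may differ is its timing: patient-paced in the intervention arm, tied to the end of the message in the control arm. Recorded durations are not given. The synopsis only caps each message at 1 minute, so the spoken messages need not end at the same time.

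4. **Does another safeguard close the gap?** Not fully. The exclusion in Sections 7.1 and 7.4 applies to knowing the assigned message beforehand and does not reach inference during the procedure. No check of whether caregivers stayed blind is described.

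5. **Do caregivers need the content in phase 1?** Not for the tasks in Section 8.2, which are to prepare the arm, wait for the finger and puncture. The instructions in Section 8.4 to act naturally, not refer to the study and not comment early can be given without it.

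6. **Could spill-over of positive wording be examined afterwards?** Only in part. Caregiver behaviour is rated in both phases and interactions are logged, but the caregiver study number is recorded only in phase 2 (Sections 5.2 and 6.1). Phase 1 data therefore cannot be grouped by caregiver.

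**The case against.** The strongest reply is that nothing in the documents shows caregivers being unblinded. The gesture is identical in both arms. The audio goes through earphones, or headphones as the alternative (Section 3.7), and nothing says that caregivers hear it. The intervention recording also places the signal after the message has been heard, so what remains is a variation in delay that is mixed up with differences between patients. Caregivers are told to act naturally, and their behaviour is rated. The ratings exposed are secondary and belong to an exploratory objective (Section 4.3). Section 6.1 also says that the study depends on caregivers' full understanding and cooperation, which is a reason to inform them.

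Most of this stands, and it limits the point to a risk. It does not remove it: the difference in closing instructions is real, the briefing makes it interpretable, and the caregiver's tasks do not require the content. The need for cooperation can be met by a briefing on logistics.

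Two stronger readings should be resisted. A reader might infer that staff are handed the message texts before phase 1 and can tell the arm from the signal. The documents mention the scripts for caregivers only in phase 2, and describe no cue that identifies the arm. A reader might also compare the lengths of the two printed messages and conclude that the recordings differ in duration. The printed texts are in English, participants must communicate in French, and no recorded durations are given, so that comparison says little.

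**Conclusion.** The point holds as a modest, avoidable weakness. Briefing caregivers on message content in phase 1 leaves their blind open to inference from the timing of the signal, and allows the positive wording to spread to both arms. It could affect the caregiver-rated secondary outcomes and caregiver behaviour. Patients rate the primary outcomes and are not told that communication is being tested, so any effect on those ratings would have to run through what caregivers do.

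The size cannot be estimated. The documents give neither the share of caregivers who might guess the arm nor the shift in rating that a guess would cause, and any figure would be the product of two assumptions. The conclusion rests on two assumptions of its own: that the phase 1 briefing is detailed enough to convey how the messages end or how the positive one is worded, and that the delay before the signal differs visibly between arms. Neither is stated in the plan.

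**What to change.** In Sections 6.2.3 and 8.4, limit the phase 1 session and the report that follows it to logistics: the patient wears earphones, wait for the finger signal, act naturally, make no comment on the study. Give message content and key elements to staff only at the start of phase 2, when they are trained to deliver the messages. The plan already has a separate session for each phase, so this moves material from one session to the other.

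The closing instructions can stay as they are. Sections 8.1.1 and 8.1.2 list control, and the lack of it, among the key elements of the messages, so aligning the signals would change what is being compared. The timing difference would remain, but caregivers would have less basis for interpreting it. If the recordings are also matched for duration, they should be set so that the spoken messages end at the same time after the start of play. Silence added at the end would not do this, because patients respond to the end of the speech or to their own readiness.

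The cost is one edited briefing and report. The small downside is that staff know less about the study during phase 1.

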8.5 Data Collection and Follow-up for withdrawn participants

In cases where patients ultimately refuse to sign the consent form or are excluded from the study, data collected in the study will be physically destroyed by a shredder, with the exception of data related to sex and age that will be reported for statistical purposes (Appendices 7 and 8). Patients will be given a copy of the complete information sheet so that they can contact the principal investigator if they wish to do so.

8.6 Trial specific preventive measures

Non-applicable.

8.7 Concomitant Interventions (treatments)

Non-applicable.

8.8 Study Drug / Medical Device Accountability

Non-applicable.

8.9 Return or Destruction of Study Drug / Medical Device

Non-applicable.

9. STUDY ASSESSMENTS

9.1 Study flow chart(s) / table of study procedures and assessments

See « Study Schedule » section.

9.2 Assessments of outcomes

9.2.1 Assessment of primary and secondary outcomes

The primary outcomes, the intensity and unpleasantness (emotional component) of pain experienced by patients during the PIC insertion, will be measured using a Visual Analog Scale (VAS) (Lang et al., 2014; Pagé et al., 2012). Patients' anxiety, as a secondary outcome, will also be measured by VAS. These three measurements will be performed by using three rulers after the PIC is inserted. These three rulers, with three different color codes to distinguish them, will be presented to the patients who will move the three sliders on a line going from one extreme to the other (No pain / Worst pain imaginable; Experience not at all unpleasant / Most unpleasant experience possible; Not at all anxious / Extremely anxious) and corresponding, on their other side, to a value between 0 and 100 mm on a 100 mm long line. This numerical value measured in millimetres will be reported in the CRF by the co-investigators. Patients will be asked to rate their overall feelings after the PIC insertion regarding these three aspects. The co-investigators will ensure that the caregivers do not become aware of the patients' responses.

As for caregivers' assessment of patients' pain intensity and unpleasantness and anxiety, these secondary outcomes will also be measured using the three VAS, this time in paper format and reported in the CRF after the PIC insertion. Caregivers will mark their estimation by tracing a line on each of the three VAS once they have completed their procedure, making sure that patients do not read their answers. The co-investigators will then measure the distance between the 0 extreme and the line traced by the caregivers in millimetres and report this numerical value in the CRF.

Before the PIC insertion, patients will assess the intensity and unpleasantness of any pre-existing pain and their basal anxiety level with these same three VAS. This will give a baseline value for these three measures. These values will be reported in the CRF before the PIC is inserted, along with the reason for consultation (internal medicine, traumatology or surgery) and any painkillers already given/ongoing in the ED.

Caregivers' behaviour will be assessed according to the criteria described by Kaptchuck (Kaptchuck et al., 2008) during the procedure. The algic behaviour of patients during the PIC insertion will also be evaluated using the Algoplus scale (Rat et al., 2011). These two behavioural evaluations will be the subject of a one-day « Rating » pilot phase, during which co-investigators will be asked to rate some of the same patients when a PIC is placed in order to ensure that their ratings are well correlated.

The characteristics of the procedure (location, caliber, number of attempts, difficulties and complications encountered), the demographic characteristics of the patients (sex, age, origin, level of education) and the demographic characteristics of the caregivers (sex, age) will be reported in the CRF after the PIC insertion. Patients will also be asked two questions (« Are you generally afraid of needles? », « Do you suffer from chronic pain, i.e. that has lasted for more than 3 months? ») to contextualize their VAS and chronic analgesics use will be reported.

Finally, in the second phase, a unique identifier related to the study (study number) will be assigned to each caregiver and entered in the CRF when the PIC is placed. If necessary, it will allow the data analysis by clustering patients by caregiver to account for the natural clustering of patients by caregivers and allow for a multi-level analysis of the caregiving effect. This identifier consisting of numbers and letters will be created from elements of the caregiver's personal identifiers that are not recognizable for a person who has not been involved in the study (e.g. D_F9B0). The identifying elements themselves will not be collected. The coding key for this study number will only be known to co-investigators collecting the data and the person in charge of monitoring the protocol. Caregivers themselves will only be informed of their code (not of the coding key). The principal investigator will not participate in data collection. When entering data into the Excel database, this study number will be coded again. That way, caregivers will not be identifiable for those performing the analysis (PI).

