5. STUDY OUTCOMES

5.1 Primary Outcomes

The primary outcome of this study will be patients' assessment of the intensity and unpleasantness (emotional component) of their pain during the insertion of the PIC.

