5.2 Secondary Outcomes

The secondary outcomes of this study will be patients' assessment of their anxiety at PIC insertion and caregivers' assessment of patients' pain intensity and unpleasantness and anxiety at PIC insertion (Singer et al., 1999).

Other co-variables will be reported in the CRF to the extent that they may influence primary or secondary outcomes:

- The intensity and unpleasantness of pain and anxiety level assessed by patients prior to the CIP;
- Reason for consultation (internal medicine, traumatology or surgery);
- Any painkillers already given/ongoing in the ED (what, when, administered by whom);
- The caregivers' behaviour during the procedure;
- The patients' algic behaviour during the procedure;
- Procedure' characteristics (location, caliber, number of attempts, difficulties and complications encountered);
- Report of a possible fear of needles (« Are you generally afraid of needles? »);
- Report of a possible chronic pain (« Do you suffer from chronic pain, i.e. that has lasted for more than three months? ») and chronic painkillers consumption.

The sex, age, origin and educational background of patients, as well as the sex and age of caregivers, will also be reported to the extent that they may influence caregivers' assessment of patients' pain intensity and unpleasantness and anxiety level (Li et al., 2001; Nevin, 1996; Singer et al., 1999).

Finally, in the second phase, a unique coded number related to the study (study number) will be assigned to each caregiver and reported in the CRF when the PIC is inserted. If needed, it will allow the analysis of data by grouping patients by caregiver.

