11.1 Hypothesis

First null hypothesis: The recorded intervention message has an effect comparable to that of the recorded control message on the painful feeling induced by the insertion of a PIC.

First alternative hypothesis: The recorded intervention message reduces the intensity and unpleasantness of the pain induced by a PIC insertion of at least 13 mm from the recorded control message.

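### The instruction for the primary VAS asks for overall feelings after the insertion, not pain caused by it, so pre-existing pain can enter the score and dilute the comparison

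*Combined protocol and SAP*

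**What the plan says.** **Target.** Section 5.1 defines the primary outcome as "patients' assessment of the intensity and unpleasantness (emotional component) of their pain during the insertion of the PIC". The alternative hypothesis in 11.1 is that the recorded intervention message "reduces the intensity and unpleasantness of the pain induced by a PIC insertion of at least 13 mm". For anxiety, 5.2 names the patients' "assessment of their anxiety at PIC insertion".

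**Measurement.** Section 9.2.1 opens by saying that the rulers measure pain experienced during the insertion. Its sentence on what patients are asked reads: "Patients will be asked to rate their overall feelings after the PIC insertion regarding these three aspects". The end points of the two pain rulers are "No pain / Worst pain imaginable; Experience not at all unpleasant / Most unpleasant experience possible"; neither mentions the catheter. Before the insertion, "patients will assess the intensity and unpleasantness of any pre-existing pain and their basal anxiety level with these same three VAS". The variable list in 6.1 describes the patient's VAS item in the same terms before and after the insertion.

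**Analysis.** Section 11.4.2 compares the VAS recorded after the insertion by t-test or Wilcoxon rank sum test. There is no change score and no baseline adjustment. The baseline ratings appear in 5.2 as co-variables that may influence the outcomes, but no analysis in 11.4 uses them.

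**The concern.** Outcome, hypothesis and instruction should have the same referent, and here they do not. Pain on arrival is not an exclusion criterion in 7.1, and trauma and surgical consultations are among the recorded reasons for attendance. A patient with a painful injury who takes the instruction literally can give the injury pain a second time, whatever the cannulation felt like. Nothing in the supplied text tells that patient to leave it out.

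The message is not aimed at the pain the patient came with. To the extent that this pain enters the score, it adds variation and pulls the between-arm difference towards zero. A null result could then mean that the message does nothing for insertion pain, or that the score did not isolate insertion pain. The instruction covers both primary ratings in both phases, and an ambiguous rating cannot be repaired once given. The anxiety ruler has a similar, lesser problem: the outcome is anxiety at insertion, but the instruction can be answered with anxiety once the procedure is over.

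**Working it through.** **1. The plan's own figure (11.2).** Inputs: difference 13 mm, SD 24 mm, alpha 0.05, power 80%, 1:1 allocation.

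- Normal approximation: n per arm = 2 × (1.960 + 0.842)² × 24² / 13² = 2 × 7.85 × 576 / 169 = 53.5, so 54.
- Two-sample t-test, two-sided: 54.48, so 55 per arm, as stated. Power at 55 per arm is 80.4%.

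The sample size reproduces. The point concerns what is measured and does not show this number to be wrong.

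**2. How merging pains dilutes the difference.** Let I be insertion pain and B background pain.

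- *Average rule*, score = (I + B)/2: a patient who merges the two contributes half the effect. If a fraction m of all patients merges, the expected difference is 13 × (1 − m/2). For m = 0.30 this is 11.05 mm; for m = 0.60 it is 9.1 mm.
- *Worse-pain rule*, score = max(I, B): a patient whose B exceeds I under either message contributes nothing. There is no simple closed form, so this was simulated.

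**3. Simulation.** Two million draws per arm. Insertion pain was beta-distributed on 0 to 100 mm with mean 34 and SD 24 (control) or mean 21 (34 − 13) and SD 21.6 (intervention). Background pain was present in 30% to 60% of patients, with mean 40 or 50 mm and SD 20, equally in both arms. Power is for a two-sided t-test at 55 per arm. Only the 34, 24 and 13 mm and the 55 per arm come from the plan. The documents give no prevalence or severity of background pain, no rule by which patients combine pains, and no share who would do so; these are assumptions.

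| Patients with background pain who merge it | Rule | Difference (mm) | Power |
|---|---|---|---|
| None | – | 13.0 | 84% |
| A quarter | average | 12.5 to 12.0 | 83% to 80% |
| A quarter | worse pain | 12.4 to 11.6 | 79% to 69% |
| Half | average | 12.0 to 11.0 | 81% to 76% |
| Half | worse pain | 11.8 to 10.1 | 74% to 55% |
| All | average | 11.1 to 9.1 | 78% to 68% |
| All | worse pain | 10.6 to 7.2 | 64% to 33% |

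The reference is 84%, not 80%, because the smaller SD in the intervention arm gives a pooled SD of √((24² + 21.6²)/2) = 22.8 mm. Losses should be read against 84%.

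**4. Second set of assumptions.** With SD 24 in both arms, background pain in 25% to 50% of patients, mean 20 to 50 mm and SD 24, and all of them using the worse-pain rule, the difference is 11.9 to 8.0 mm. Power is 72% to 34%, against 81% without contamination (normal approximation). The direction is the same and the range as wide.

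**5. What baseline adjustment could do.** Suppose 24 mm is already the SD of the score as patients give it, and the full 13 mm difference remains. Adjusting for a baseline with correlation r reduces the SD to 24 × √(1 − r²). For r = 0.3, 0.5 and 0.7 this is 22.9, 20.8 and 17.1 mm, and power at 55 per arm is 85%, 91% and 98% (normal approximation). Adjustment removes noise; it does not restore a difference that has already been diluted.

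**The case against.** The best defence is that the sentence is loose, not wrong. Section 9.2.1 begins with pain during the insertion, and the instruction refers back to those aspects. "After" may be only the time at which the rating is taken, and "overall" may mean the whole procedure, which can take several attempts. The baseline rating is given its own target, pre-existing pain, so the authors do distinguish the two. Patients must communicate in French, so the spoken question is presumably not this sentence, and the CRF text is not among the supplied material. All of this stands, and it limits confidence to moderate. It does not remove the need for agreement: the opening sentence of 9.2.1 describes the construct and is not addressed to the patient, and 11.4.2 and 11.5 also speak of pain after the insertion.

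A reader might infer four stronger things that the documents do not support:

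- *That the score does contain pre-existing pain.* The text permits this; it does not establish it.
- *That the comparison is biased.* Randomisation balances pre-existing pain in expectation.
- *That the 34 mm mean and 24 mm SD belong to a different quantity.* They come from cited studies whose rating questions cannot be seen here and which may already carry background pain.
- *That tourniquet discomfort contaminates the score in the same way.* The order of steps in 6.1 puts the baseline rating before the tourniquet, and only the control message describes how it feels. Any effect would tend to widen the difference, not shrink it. Section 8.1.2 lists that sensation as a key element of the control message, so it is arguably part of the contrast under test. What is missing is a statement of whether it counts.

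**Conclusion.** The mismatch holds. The only rating instruction in the supplied text does not limit the primary VAS to pain during, or induced by, the insertion, and the primary analysis uses the raw score. The consequence is possible dilution and noise, and a null result that is harder to read.

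Its size cannot be fixed from the documents. Under the assumed prevalence and severity, it runs from almost nothing (80% to 83% if a quarter of affected patients average the two pains) to severe (33% at the extreme where all of them report the worse pain). The share of patients who merge the two pains is the main unknown, so the low figures are an upper end of the loss and not an expectation. This is a recommended fix before enrolment, at moderate confidence, subject to a check of the CRF wording.

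**What to change.** 1. Check the question as worded in both CRFs (Appendices 4 and 5).
2. In 9.2.1 and both CRFs, replace the sentence with a fixed script, read identically in both arms. It should ask for the pain caused by placing the catheter, and separately its unpleasantness, and say that the pain the patient came with is not meant. For anxiety, it should ask about the moment of placement. A fixed script also helps in the second phase, where only patients are blinded.
3. State whether tourniquet discomfort counts as part of the procedure being rated.
4. Align the wording of 5.1, 9.2.1, 11.1 and 11.4.2.
5. As a complement, prespecify in 11.4.2 that the primary comparison is adjusted for the matching baseline VAS (for example by ANCOVA).

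The cost is a short text in the protocol and each CRF, a sentence in the analysis section and a short briefing of the co-investigators. It needs no additional patients, visits or measurements, because the baseline ratings are already collected.
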